### 1.4.4. Analysis of Secondary Judgment Criteria

Quantitative secondary criteria to be compared between the two treatment arms (criteria 1 to 7, 12, and 13) will be analyzed using multiple linear regression with a center effect and an adjustment for the initial value of the parameter being studied.

Judgment criterion number 8 (change in the average number of steps per week) will be assessed graphically and using mixed linear regression with weekly steps as the dependent variable, with the randomization arm and time (from D0-2 weeks to D0+8 weeks) as fixed effects, and the patient as a random effect. The p-value for the interaction term will be used to assess the significance of the evolution based on the treatment arm. The same type of analysis will be used for criteria 9 and 10.

Qualitative criterion 11 will be analyzed as the primary judgment criterion.

Criteria 14 to 17 will be analyzed using descriptive statistics as described in section 2.4.1.

# **1.5. Statistical Significance Level**

Alpha risk set at 5%.

### 1.6. Method for Handling Missing, Unused, or Invalid Data

Analyses will be performed on complete data. If missing data for the primary judgment criterion exceeds 10%, a sensitivity analysis will be conducted after multiple imputation.

### 2. Modifications Made to the Protocol's Analysis Plan

### **Definition of the PP Population:**

The protocol and the SAP did not specify the definition of the per-protocol population. This population includes all randomized patients who:

- Received the medical device and adhered to the randomization arm,
- Met the eligibility criteria,
- Were adherent, meaning they followed at least 80% of the scheduled sessions, i.e., 2 sessions of 30 minutes per day during the first 2 months of follow-up.

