# 1.4.3. Analysis of the Primary Judgment Criterion

The primary judgment criterion will be analyzed using logistic regression with a center effect. A Per Protocol sensitivity analysis will be conducted, including only patients who adhered to the medical device. A patient will be considered adherent if they completed more than 80% of the planned sessions, considering a low-frequency usage of 2 sessions per day.

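### The SAP says no per-protocol population had been defined, but its own section 1.4.3 gives a membership rule, which section 2 changes without giving a reason or a date

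*SAP*

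**What the plan says.** SAP section 1.4.3 plans the analysis and says who is in it: "A Per Protocol sensitivity analysis will be conducted, including only patients who adhered to the medical device". It then makes adherence countable: "A patient will be considered adherent if they completed more than 80% of the planned sessions, considering a low-frequency usage of 2 sessions per day". It sets no other condition and no explicit time window.

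SAP section 2, which lists modifications to the plan, opens its entry on this population with "The protocol and the SAP did not specify the definition of the per-protocol population". It then asks for two things beyond adherence: the patient must have been given the device and kept to the allocated arm, and must have satisfied the entry criteria. The adherence condition itself is reworded: "Were adherent, meaning they followed at least 80% of the scheduled sessions, i.e., 2 sessions of 30 minutes per day during the first 2 months".

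The protocol synopsis supplied contains no per-protocol rule. The only other sensitivity analysis of the primary endpoint is multiple imputation, which SAP section 1.6 triggers only when more than 10% of primary outcomes are missing.

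**The concern.** A modifications section should tell the reader what was planned, what replaced it and why. Neighbouring entries do this: those on the primary model and on the quantitative secondary criteria name the planned method and say why it was not used. The per-protocol entry instead says there was nothing to replace, so a changed rule reads as the filling of a gap.

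Section 2 was written with data in hand. It reports that a single centre enrolled every patient and that criterion 11 came out the same in both groups. The documents do not say whether the per-protocol rule was settled before or after outcomes by arm were known. A reader who relies on the opening sentence has no reason to ask.

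What is at stake is the one robustness check on the primary endpoint that is always run. At the design rates in SAP section 1.3 (15% against 0.1%, 30 per arm), the expected responders are 30 × 0.15 = 4.5 with VERUM and 30 × 0.001 = 0.03 with SHAM. With so few, it matters that membership of the set is fixed in advance and traceable.

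**Working it through.** The documents give no per-protocol count to reproduce. Their only design figure, 30 per arm, follows from the arcsine formula: h = 2·asin(√0.15) − 2·asin(√0.001) = 0.732; n = 2 × ((1.960 + 0.842)/0.732)² = 29.3, rounded up to 30, with power 80.9%. The point here does not depend on it.

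**Step 1: the two rules side by side.**

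| Element | SAP 1.4.3 | SAP section 2 |
|---|---|---|
| Threshold | above 80% | 80% or above |
| Sessions due | 2 per day | 2 per day, 30 minutes each |
| Window | not stated | first 2 months |
| Eligibility met | not required | required |
| Device received, arm kept | not required | required |

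**Step 2: the threshold.** With D days, N = 2D sessions are due. The inclusive rule needs the smallest whole number not below 0.8N; the strict rule needs the smallest whole number above 0.8N. They differ, by one session, only when N is a multiple of 5.

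| Days | Due | 80% of due | Inclusive needs | Strict needs |
|---|---|---|---|---|
| 56 | 112 | 89.6 | 90 | 90 |
| 59 | 118 | 94.4 | 95 | 95 |
| 60 | 120 | 96.0 | 96 | 97 |
| 61 | 122 | 97.6 | 98 | 98 |
| 62 | 124 | 99.2 | 100 | 100 |

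The rules also coincide at 57 days (114 due, both need 92) and 58 days (116 due, both need 93). Across 56 to 62 days, only a patient with exactly 96 of 120 sessions on a 60-day count is classified differently.

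**Step 3: the window.** Section 1.4.3 concerns an endpoint measured 2 months after randomization, so J0 to M2 is its natural window. Section 2 makes that explicit, which is a clarification. The choice would matter only if 1.4.3 were read over all six months of use. Taking 180 days (360 sessions due), a patient with 110/120 and then 150/240 has 91.7% to M2 but 260/360 = 72.2% overall. One with 90/120 and then 220/240 has 75.0% and 310/360 = 86.1%.

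**Step 4: direction of each change, counted J0 to M2.** The inclusive threshold can only add patients, namely those at exactly 80%. The eligibility, arm and session-length conditions can only remove them. Requiring receipt of the device changes nothing in practice, since a patient without it cannot reach 80%. The documents report no number of patients affected by any of these conditions.

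**The case against.** The best defence is that section 1.4.3 defines an adherent patient, not a full population, and that section 2 completes it with conventional conditions while keeping the 80% level and the two-a-day count. Section 2 is labelled as modifications, both texts are in the same document, and the sentence is correct for the protocol as supplied. The analysis is a sensitivity analysis in a self-described pilot.

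Much of this stands. A reader might infer that two definitions are in force together; they are not, because section 2 supersedes section 1. A reader might also infer that the new rule was chosen for its result. The past-tense wording elsewhere in section 2 shows when that section was written, not when this rule was set, so the documents do not support the inference. The 30-minute wording may only restate the treatment schedule in the protocol.

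The defence fails on the main sentence. In section 1.4.3 adherence is the sole condition for entering the analysis, so it is a membership rule, and the SAP did specify one. Calling the entry a modification does not help when the entry denies that there was anything to modify.

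**Conclusion.** The statement in section 2 is inaccurate for the SAP. A pre-stated rule was changed in its threshold and supplemented with further conditions, without a reason or a date relative to unblinding. Different patients could enter the per-protocol set as a result.

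The size is unknown and should not be overstated. A reader might infer that different patients did enter, or that the change from above 80% to 80% or above probably altered the conclusion. The documents support neither. They report no adherence data, no ineligible or arm-deviating patients and no per-protocol counts, and the threshold wording affects at most a patient at exactly 96 of 120. Any material difference would come from the eligibility, arm and session-length conditions. This assumes that section 1.4.3 is read over J0 to M2. The primary analysis is not touched; this is a correction that should be made to keep its one unconditional sensitivity analysis traceable.

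**What to change.** 1. Replace the opening sentence of the section 2 entry with a statement that it changes the rule in section 1.4.3. Name each change, give the reason, and give the date relative to unblinding.
2. Run the per-protocol analysis on the section 1.4.3 rule, counted J0 to M2, and report it as the pre-specified sensitivity analysis.
3. Show the section 2 set beside it, labelled as a later modification.
4. Report per arm how many patients differ between the two sets. If none do, one line to that effect is enough.

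The device log file already records session counts and durations (SAP section 1.2.2, criterion 17), so the cost is a text correction and one extra model run. The small downside is a second per-protocol result, which may be less favourable.

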### **Description of Baseline Characteristics:**

In accordance with current recommendations, baseline group comparisons were not performed.

### Analysis of the Primary Criterion:

All patients in the study were included by the HFAR center, so a fixed-effects logistic regression was conducted instead of the initially planned random-effects center logistic regression.

### Analysis of Secondary Criteria:

- Secondary analyses were conducted on the ITT population and available data, with no imputation performed.
- Since the distribution of quantitative secondary judgment criteria (criteria 1 to 8, 12, and 13) did not follow a normal distribution, the originally planned linear regressions were not performed. Instead, median differences and their 95% confidence intervals, calculated using the Mood method, were used for comparisons between the two treatment arms. The variation between scores at each time point and the initial score was also calculated when the baseline score was available.
- The protocol was not followed for criterion 8 (evolution of the average number of steps per week) because very few patients agreed to wear the Fitbit watch, and it was given to them simultaneously with the device. Consequently, the before/after comparison of wearing the bracelet could not be performed. Available data was described for informational purposes only.
- Criterion 11 (percentage of patients without treatment modification) was not analyzed using a logistic model, as the results were identical between the two groups.
- Heart rate and sleep hours (criteria 9 and 10) were not analyzed due to the absence of data.

Secondary analyses are exploratory, and no alpha risk adjustment for multiplicity was performed.

All statistical analyses were performed using R software (version 4.3.0).

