	using an activity tracker (Fitbit 4) between -2 weeks and +8 weeks, for patients who agreed to wear this second bracelet. 10. Evolution of the average weekly heart rate measured using an activity tracker (Fitbit 4) between -2 weeks and +8 weeks, for patients who agreed to wear this second bracelet. 11. Percentage of patients with no change (in drug type or dosage) or a decrease in medication dosage. 12. Score on the Clinical Global Impression of Change (CGI) questionnaire (Annex 8) at M2, taking J0 as the reference point, reported in person or by phone by the person identified by the patient as the primary caregiver. 13. Score on the Clinical Global Impression of Change (CGI) questionnaire (Annex 8) at M2, taking J0 as the reference point. 14. CGI score at M6, taking M2 as the reference, then every 2 weeks for two months via phone interviews. For phone assessments, the patient will be asked to use the situation from two weeks prior (during the previous CGI score evaluation) as the reference. 15. Description of adverse events reported during the study: number, intensity, severity, duration in each of the two arms. 16. Acceptability and usability questionnaire completed by the patient at M6 (Annex 10). 17. Compliance assessed using the medical device log file (number of sessions/day, duration of sessions, start and end times, pause times).
Study design	Multicenter, controlled, randomized, parallel two- arm, double-blind efficacy trial. Randomization will be performed with a 1:1 ratio and will be stratified by center.
Population	Patients will be recruited via neurology consultations for the management and monitoring of their Parkinson's disease.
Selection criteria	 Patient aged over 18 years Follow-up for Parkinson's disease with progression for more than 5 years Stable treatment for at least 3 months Maintained sufficient autonomy to participate in the study Non-faller: Hoehn and Yahr score in ON DOPA <4 (Annex 9) Informed and has signed consent to participate in the study Affiliated or beneficiary of a social security scheme

	Negative urinary pregnancy test for women who are not postmenopausal
	Exclusion Criteria

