Inclusion Visit (J0-2 to -4 weeks)

- Verification of inclusion and non-inclusion criteria
- Information and obtaining written informed consent from the patient
- Information to the patient regarding the Fitbit 4 and the option to use it
- Trial fitting of the Remedee Endorphin Band device

Visit 1 (J0)

- Confirmation of patient's willingness to participate
- Randomization
- Provision of the medical device and instructions on its use
- Administration of the various assessment tests (if necessary, after administration of Modopar dispersible):
 - o MDS-UPDRS (I, II, III, and IV)
 - o PDQ39
 - o KPPS
 - o SWS

Phone Call at J7 and M1: Verification that the patient does not encounter any difficulties in using the device (call by the TEC)

Visit 2 (M2)

- Administration of the various assessment tests (if necessary, after administration of Modopar dispersible):
 - o MDS-UPDRS (I, II, III, and IV)
 - o PDQ39
 - o KPPS
 - o SWS
- CGS score from the caregiver (in-person or by phone)
- CGS score from the patient

	 Retrieval of usage data from the medical device (log file) Retrieval of the first medical device (active or inactive) and provision of an active medical device to all patients. Visit 3 (M4) Administration of the various assessment tests (if necessary, after administration of Modopar dispersible): MDS-UPDRS (I, II, III, and IV) PDQ39 KPPS SWS Retrieval of usage data from the medical device (log
	file) Visit 4 (M6) • Administration of the various assessment tests (if necessary, after administration of Modopar dispersible):
	 KPPS KPPS SWS Administration of the acceptability and usability questionnaire for the medical device CGS score from the patient Retrieval of usage data from the medical device (log file) Retrieval of the millimeter-wave emitting bracelet Retrieval of the Fitbit4 for patients who accepted its use
	Phone Calls at M6+2 weeks, M6+4 weeks, M6+6 weeks, and M6+8 weeks: CGS score from the patient, and at M6+8 weeks, the patient will also be asked if they would have liked to continue using the medical device bracelet.
Sample size	60 (30 per arm)
Statistical analysis	The primary endpoint will be analysed using logistic regression with a centre effect.
Planning	Enrollement : 24 months Study participation for each patient : 8 months Total study length : 32 months

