### 1.2.2. Secondary Judgment Criteria

1. Mean change in MDS-UPDRS III score in ON Dopa conditions.

- 2. Mean change in MDS-UPDRS I score (Appendix 2) in ON Dopa conditions.
- 3. Mean change in MDS-UPDRS II score (Appendix 3) in ON Dopa conditions.
- 4. Mean change in MDS-UPDRS IV score (Appendix 4) in ON Dopa conditions.
- 5. Mean change in the Parkinson Disease Questionnaire -39 (PDQ 39) score (Appendix 5) in ON Dopa conditions.
- 6. Mean change in King's PD Pain Scale (KPPS) score (Appendix 6) in ON Dopa conditions.
- Change in the time (in seconds) required for the Stand-Walk-Sit (SWS) test (Appendix 7) in ON Dopa conditions. This change will be expressed as a percentage of time change, defined as the difference between the time required at baseline and 2 months after randomization, divided by the baseline time.
- 8. Slope of the change in the average number of steps per week measured with an activity bracelet (Fitbit 4) between D-2 weeks and D+8 weeks, for patients who agreed to wear this second bracelet.
- 9. Evolution of the average number of hours of weekly sleep and the average weekly hours of deep, paradoxical, light sleep, and night wakefulness, measured with an activity bracelet (Fitbit 4) between D-2 weeks and D+8 weeks, for patients who agreed to wear this second bracelet.
- 10. Evolution of the average weekly heart rate measured with an activity bracelet (Fitbit 4) between D-2 weeks and D+8 weeks, for patients who agreed to wear this second bracelet.
- 11. Percentage of patients without any modification (in drug molecule or dosage) in their medication regimen or with a reduction in medication dosage.
- 12. Score on the Clinical Global Impression of Change (CGI) questionnaire (Appendix 8) at M2, using the baseline (D0) provided in person or by phone by the person designated as the primary caregiver.
- 13. Score on the CGI questionnaire (Appendix 8) at M2, using D0 as the reference.
- 14. CGI score at M6, using M2 as the reference, and then every 2 weeks for two months through phone interviews. For phone evaluations, the patient will be asked to use the situation two weeks prior (during the previous CGI score evaluation) as the reference.
- 15. Description of adverse events reported during the study: number, intensity, severity, duration in each arm.
- 16. Acceptability and usability questionnaire completed by the patient at M6 (Appendix 10).

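### Criteria 12 and 13 (global impression of change) have no initial value to adjust for, and the Mood median difference that replaced the planned regression is a weak comparison for them

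*SAP*

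**What the plan says.** The protocol synopsis introduces criterion 12, the primary caregiver's rating, with "Score on the Clinical Global Impression of Change (CGI) questionnaire (Annex 8) at M2, taking J0 as the reference point, reported in person or by" (quotation cut there; the sentence goes on to name the caregiver as the source). SAP section 1.2.2 defines criterion 13, the patient's own rating, as "Score on the CGI questionnaire (Appendix 8) at M2, using D0 as the reference".

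SAP section 1.4.4 puts both among the "Quantitative secondary criteria to be compared between the two treatment arms (criteria 1 to 7, 12, and 13") and assigns them "multiple linear regression with a center effect and an adjustment for the initial value of the parameter being studied".

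SAP section 2, under Analysis of Secondary Criteria, gives one reason for abandoning that model: "Since the distribution of quantitative secondary judgment criteria (criteria 1 to 8, 12, and 13) did not follow a normal distribution". In its place, "median differences and their 95% confidence intervals, calculated using the Mood method, were used for comparisons between the two treatment arms". The same section says that change from the initial score was computed where a baseline existed, and that secondary analyses are exploratory with no multiplicity adjustment. It is written in the past tense, as a record of analyses already carried out.

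**The concern.** A rating of change since D0 has no D0 value, so the model in section 1.4.4 is undefined for these two criteria. The SAP amends the model without noticing this, because the reason it gives is the shape of the distribution.

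The replacement then treats a single global rating in the same way as multi-item totals such as the MDS-UPDRS parts. If the rating has only a few categories, many patients tie at the median. The median difference then moves in half or whole categories and can be exactly zero although VERUM ratings have shifted. The Mood comparison also discards most of the ordering in the data.

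Criteria 12 and 13 are how the plan measures effectiveness as perceived by caregiver and patient. In a 30-per-arm pilot such results help decide what is studied next, and a median difference of zero could be misread as no perceived benefit.

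**Working it through.** **1. Is there an initial value?** In the protocol, under Conduct of the trial, Visit 1 (J0) lists MDS-UPDRS I to IV, PDQ-39, KPPS and SWS, and no global rating. Visit 2 (M2) is the first to list one: "CGS score from the caregiver (in-person or by phone"), followed by the patient's score. I read CGS there as the CGI of the outcome list. Even if the question were asked at D0, change from D0 to D0 is the same for everyone, and a constant covariate adjusts for nothing. So "an adjustment for the initial value of the parameter being studied" has no content for criteria 12 and 13.

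**2. The plan's own figure.** None is given for these criteria. The 30 per arm in SAP section 1.3 concerns the primary endpoint (15% v 0.1%). It reproduces with the arcsine formula: h = 2·asin√0.15 − 2·asin√0.001 = 0.795 − 0.063 = 0.732, and n = 2(1.960 + 0.842)²/h² = 29.3. It supplies only the n used below.

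**3. When does the median move?** Let p be the SHAM share rated better than no change, with the SHAM median at no change. Under a common odds ratio OR, the VERUM share is p′ = OR·p/(1 − p + OR·p). The VERUM median leaves no change only if p′ > 1/2, that is, p > 1/(1 + OR): above 33% for OR 2 and above 25% for OR 3.

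| SHAM at no change | p | p′, OR 2 | p′, OR 3 | True median difference |
|---|---|---|---|---|
| 55%, symmetric | 0.225 | 0.45/1.225 = 0.37 | 0.675/1.45 = 0.47 | 0 at both |
| 55%, tilted to improvement | 0.28 | 0.56/1.28 = 0.44 | 0.84/1.56 = 0.54 | 0, then 1 category |
| 40% | 0.35 | 0.70/1.35 = 0.52 | 1.05/1.70 = 0.62 | 1 category at both |

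The same treatment effect thus gives a median difference of zero or of one category, depending only on the SHAM distribution.

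**4. Simulated power, 30 per arm.** Assumptions: the number of categories, the SHAM distributions and the proportional-odds shift. Mood is Fisher's exact test on the split at the pooled median, with ties counted as low or as high. Wilcoxon uses the normal approximation. Linear is a two-sample t-test, which is the planned model without the baseline term and with one centre. Each row is 3,000 trials at OR 3; the Monte Carlo standard error is at most √(0.25/3000) = 0.9 points.

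| SHAM distribution (%) | Mood, ties low | Mood, ties high | Wilcoxon | Linear | Equal medians |
|---|---|---|---|---|---|
| 7 levels: 1/5/14/50/20/8/2 | 26% | 37% | 60% | 58% | 72% |
| 7 levels: 2/8/25/40/17/6/2 | 33% | 37% | 65% | 62% | 9% |
| 5 levels: 3/17/50/25/5 | 27% | 39% | 61% | 60% | 71% |
| 11 levels, bell-shaped | 43% | 41% | 65% | 64% | 7% |
| 101 levels, bell-shaped | 43% | 44% | 67% | 66% | 0.3% |

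At OR 1, type I error on 5 to 7 levels is about 2-3% for Mood and 4-5% for Wilcoxon and the linear comparison.

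**5. Range over SHAM shapes, 7 levels, OR 2 to 3.** Mood has 6-35% power (ties low) or 15-41% (ties high), and Wilcoxon has 28-64%. Sample medians are equal in 92% to 62% of trials with 55% symmetric at no change, in 69% to 26% with the 55% tilted to improvement, and in 43% to 10% with 37% at no change. Another spread of the remaining ratings in the 37% case gave 36% to 8%.

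**The case against.** - **The regression was never run.** True, so the live question is the Mood analysis. The remark that change was computed where a baseline existed hints that some criteria lack one, but it does not correct section 1.4.4.
- **The scale is not shown.** This stands: 7 categories is an assumption. The loss of power does not depend on it (43% v 65% on 11 levels), but frequent equal medians do.
- **The size is sensitive to assumptions.** This stands. Equal medians run from 92% to 10%, and Mood power depends on the tie rule, which the SAP does not state. The simulation also uses a Mood test, whereas the SAP reports an interval.
- **An ordinal outcome does not rule out linear regression.** A reader might infer that the planned model was wrong because the CGI is ordinal. The check does not support that: without the baseline term, a linear comparison comes within about 3 points of Wilcoxon and keeps its type I error near 5%. Only the missing baseline blocks the model.
- **Other patient-reported measures exist.** A reader might take these two criteria as the only evidence of patient-perceived benefit. Daily-life experiences, PDQ-39 and pain (criteria 2, 3, 5 and 6) are also compared between arms.
- **Section 1.4.1 already plans counts and percentages.** It does so for qualitative variables, but section 1.4.4 classes these criteria as quantitative, so a category table is not clearly promised.

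**Conclusion.** The point holds in a limited form. From the documents alone, the baseline adjustment cannot be applied to criteria 12 and 13, and the SAP never says so. On the assumptions of about 7 categories, 30 per arm and a common odds ratio of 2 to 3, the Mood comparison gives up much of the power of a rank analysis under either tie rule. Its median difference may or may not be zero for the same effect, according to how SHAM patients rate themselves.

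It would go too far to say that the median difference will usually be zero, or that a perceived benefit has been missed. The first depends on an unknown SHAM distribution; for the second, the documents contain no CGI results. The criteria are exploratory, each median difference comes with a 95% CI, and the primary analysis is untouched.

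**What to change.** Amend the SAP for criteria 12 and 13 as follows.

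1. Remove both from the baseline-adjusted set in section 1.4.4 and state that no initial value exists.
2. State the CGI categories and their order, and use one name for the scale across the documents.
3. Compare arms by Wilcoxon-Mann-Whitney. Report a proportional-odds common odds ratio (or the probability of superiority) with 95% CI, without baseline adjustment.
4. Show the number and percentage in every category by arm.
5. Label this a post hoc change to exploratory analyses, since section 2 reports the analyses as done. Keep the Mood result alongside, with its tie rule stated.

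The cost is SAP wording and two short analyses of data already held. The downside is the post hoc label, because the method would be chosen after results may be known.

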# 1.4. Description of Statistical Methods

# 1.4.1. Descriptive Analysis

A flowchart, created according to CONSORT guidelines, will summarize the number of patients screened, included, randomized, lost to follow-up, and analyzed for each randomization arm. The reasons for non-participation at each step will be described. A descriptive analysis of the data will be performed. This will include point estimates,

numbers, and percentages for qualitative variables, mean, standard deviation, median, and range for quantitative variables. The normality of continuous variables will be assessed graphically and using a normality test (e.g., Shapiro-Wilk). A description of missing data for each variable (sample size and percentage) will also be provided.

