# 1.4.2. Comparison at Baseline

Comparability at baseline between the experimental and control arms will be assessed using a Student's t-test (or Wilcoxon-Mann-Whitney test if needed) for continuous parameters and a Chi-square test (or Fisher's exact test if necessary) for qualitative parameters.

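### Criteria 1–7: non-normal outcomes alone do not justify replacing the planned baseline-adjusted regression with Mood median differences; restoring it is a free improvement

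*SAP*

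**What the plan says.** **Planned.** SAP section 1.4.4 assigns criteria 1–7, 12 and 13 to "multiple linear regression with a center effect and an adjustment for the initial value of the parameter being studied". It names no fallback for non-normal outcomes. Section 1.2.2 defines criteria 1–6 as mean changes, for example "Mean change in MDS-UPDRS III score in ON Dopa conditions". Criterion 7 is a percentage change in walking-test time and is not called a mean.

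**Normality.** Section 1.4.1 says "The normality of continuous variables will be assessed graphically and using a normality test (e.g., Shapiro-Wilk"). This belongs to the descriptive analysis. It concerns the variables, not model residuals, and no rule links it to dropping a model. A rank-test alternative is named only in section 1.4.2, for the baseline comparisons.

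**Changed.** SAP section 2, under the secondary criteria, gives the reason: "Since the distribution of quantitative secondary judgment criteria (criteria 1 to 8, 12, and 13) did not follow a normal distribution". It continues that "the originally planned linear regressions were not performed. Instead, median differences and their 95% confidence intervals, calculated using the Mood method, were used". It adds: "The variation between scores at each time point and the initial score was also calculated when the baseline score was available". It does not say whether change or M2 scores were compared between arms, or which form of the Mood method was used. It closes the topic with "Secondary analyses are exploratory, and no alpha risk adjustment for multiplicity was performed".

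**The concern.** A change of method needs a reason that bears on the method dropped. Linear regression makes no assumption about the marginal distribution of the outcome. Normality concerns the residuals, and matters little for a two-arm contrast with equal groups of this size. If non-normality did not disqualify the regression, two planned features were given up without need:

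- the baseline adjustment, for criteria 1–7;
- the mean-change target, for criteria 1–6.

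Criterion 1 matters most, because it is the continuous form of the primary outcome in a 60-patient pilot.

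The scope is narrow. Criteria 12 and 13 are global-change scores with no initial value, so the baseline term never applied to them. Criterion 8 had its own mixed model, and section 2 gives a separate reason for abandoning it. The centre term falls away legitimately, since section 2 reports that one centre recruited every patient.

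**Working it through.** **Inputs.** From the documents: 30 per arm, 1:1 allocation, two-sided 5%. The documents give no SD, correlation, power or distribution shape for criteria 1–7, so there is no plan figure to reproduce on this point. The 30 per arm was set for the primary criterion and serves here only as the group size.

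Assumed: correlation r between baseline and M2 of 0.5, 0.65 and 0.8. The model is M2 = r × baseline + √(1 − r²) × error + effect. Baseline and error are both normal, gamma (shape 2), t4 or lognormal (sigma 1), scaled to unit variance. There were 20,000 replicates per setting.

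**Step 1. Does non-normality invalidate the planned regression?** Type I error of ordinary regression on arm and baseline, nominal 5%:

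| Setting | Type I error |
|---|---|
| 30 per arm, all four shapes | 4.2–5.2% |
| 25 per arm | 3.8–5.2% |
| Whole-number scores (assumed SD 3, 8 and 14 points) | 4.0–5.1% |
| Criterion 7 form (percentage change, lognormal times, assumed log-SD 0.2–0.5) | 4.9–5.0% |

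The level holds at about 4–5% throughout, slightly low under strong skew. A separate simulation with exponential and two lognormal outcomes gave 4.1–5.0%.

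**Step 2. What happens to precision?** The SD of the median difference was divided by the SD of the baseline-adjusted estimate (above 1 means the median is less precise).

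For normal data a large-sample check is available:

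- Change scores: variance ratio (π/2) × 2(1 − r)/(1 − r²) = π/(1 + r). At r = 0.5 this is 2.09 (SD ratio 1.45); at r = 0.8 it is 1.75 (SD ratio 1.32).
- M2 scores: variance ratio (π/2)/(1 − r²). At r = 0.5 this is 2.09 (SD ratio 1.45); at r = 0.8 it is 4.36 (SD ratio 2.09).

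Simulated SD ratios at 30 per arm, r 0.5–0.8:

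| Shape | Change compared | M2 compared |
|---|---|---|
| Normal | 1.27–1.41 | within 1.15–2.0 |
| Gamma | 1.13–1.19 | within 1.15–2.0 |
| t4 | 1.01–1.15 | within 1.15–2.0 |
| Lognormal | 0.58–0.59 | 0.8–1.2 |

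The lower end of 1.15 for M2 is t4 at r = 0.5. There the error is symmetric and change and M2 have the same distribution, so the change-score ratio applies to both.

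**Step 3. What does the nominal 95% interval mean?** If the interval inverts a Mood median test, its level depends on the variant. Without ties at 30 per arm, the hypergeometric distribution gives 6.98% for the uncorrected test and 1.94% for the exact or Yates version. With whole-number scores the simulated levels are 4.9–5.8% and 2.4–2.9%. Since the variant is not stated, coverage cannot be judged from the text.

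**The case against.** The strongest reply is that skew can be a good efficiency reason for using medians. This stands in part: with strongly skewed data the median difference on change has about 0.6 times the SD of the adjusted estimate. Non-normality is therefore not irrelevant. It fails only as a ground for treating the planned regression as unusable, and section 2 makes no efficiency argument.

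Several stronger readings are tempting, and the documents do not support them:

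- *The switch cost precision or power.* Step 2 shows that the direction depends on the distribution shape and on the quantity compared, and section 2 gives neither. Head-to-head power figures mislead as well, since they set a 5% regression test against an uncorrected Mood test running near 7%.
- *Losing the adjustment is like losing 6 to 15 of the 60 patients.* The formula 60(1 + r)/2 gives 54 at r = 0.8 and 45 at r = 0.5. It describes an unadjusted mean change, whereas medians were compared.
- *Mean changes are not reported.* The SAP says only that the regressions were not performed. Section 1.4.1 still plans means and SDs, and section 2 says change from the initial score was calculated.
- *A benefit confined to a minority would be missed.* The sample-size rationale neither states nor excludes such a pattern. Under an equal shift in all patients the median moves fully.
- *The comparison is biased, or the method was chosen for its result.* Omitting a baseline covariate in a randomised comparison does not bias it, and nothing in the text suggests a choice driven by results.

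It is also fair to say that the change is openly disclosed and that the analyses are labelled exploratory. Restoring the regression now is itself a decision taken after the distributions were seen, and more analyses per criterion add to a set with no multiplicity control. These points limit the consequence and shape the fix. They do not supply the missing justification.

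**Conclusion.** The point holds as a free improvement of low consequence. Non-normality is the only reason given for criteria 1–7, and it does not invalidate the planned baseline-adjusted regression, whose type I error stays at about 4–5% at this sample size. What was certainly given up is the planned adjustment (criteria 1–7) and the between-arm comparison of mean change (criteria 1–6). The net effect on precision is unknown: the SD ratio could lie anywhere from about 0.6 to 2.0.

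These figures rest on the assumed shapes and correlations, on an equal shift in all patients, and on the same distribution shape in both arms. The primary analysis is untouched.

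**What to change.** For criteria 1–7, report the regression on arm and baseline value with its 95% confidence interval. Omit the centre term because there was one centre. State that this analysis was restored after the distributions had been seen. A robust (HC3) interval or a rank-based ANCOVA may be added as sensitivity. Neither is required, since ordinary regression already holds its level.

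Keep the Mood median differences as a labelled supplement, and state which Mood variant was used and whether change or M2 scores were compared. Keep the exploratory label.

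The cost is one regression for each of seven criteria, on data already held, plus two sentences in section 2.
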